2.7.2 Muscle, Adjacent Organs, and Soft Tissue

The pathophysiology of radiation-related changes in muscle, organs and soft tissue are poorly understood. The clinical manifestations of treatment to doses ranging from 50-60 Gy range from fibrosis to atrophy, and often result in diminished physical function (51). Anecdotal experiences in young children suggest doses at or below 20 Gy are associated with readily discernible soft tissue alterations. Correlations have been evaluated in patients treated for breast cancer using breast conservation surgery followed by breast irradiation. Relationships have been established between radiation parameters (dose delivered to the intact breast and the volume receiving high dose radiation) and clinical cosmetic scores (52). Measurement of tissue compliance has also been used as an objective documentation of superficial fibrosis. Though not specific for a given tissue type, this technique appears to be a simple, method for determining changes in soft tissue compliance consistent with subjective grading of fibrosis (53). Evaluations of the available data suggest that the variability of site contains as much error as the ability to measure fibrosis. We will discontinue collecting tissue compliance with this amendment (amendment 5.0) and report the outcomes for the available data.

Muscle atrophy is a clinically evident phenomenon seen following radiotherapy to the soft tissues. (54). Treatment results in decreased development of major muscle groups in some patients. Correlations with radiotherapy dose and volume have been poorly defined, but this treatment effect appears to occur following large volume radiotherapy delivered to higher doses. The resultant functional effects of decreased strength and mobility are not documented. Incorporation of validated functional scales and assessments of quality of life related to function will provide needed data on the long term effects of specific dosimetric parameters. Relation of the outcome measures to radiation dosimetry through mathematical models will further our understanding of these effects and how they may be avoided in the future. Elucidation, through prospective evaluation, of possible factors affecting the formation of fibrosis, muscle atrophy and functional changes may allow improved treatment approaches with reduction of these effects in the future.

The study of basic functional changes, determined from standard imaging, clinical testing or functional scales, in individual irradiated organs is key to defining normal tissue tolerances as we move forward with increasingly conformal radiation modalities and techniques. We will continue to collect information about these toxicities and related them to dosimetry and clinical characteristics as patient numbers and organ exposure allow.

2.7.3 Vascular Changes

Tissue microvasculature and some macrovasculature are affected by radiation. Radiation induced endothelial cell proliferation and endothelial cell loss may result in thrombosis of capillaries and arterioles (17). Larger vessel injury has been reported in patients irradiated for parasellar central nervous system tumors (Moyamoya syndrome) (55), but has not been documented in the irradiation of other larger vessels. Radiation induced vascular changes may not be the primary pathophysiologic event responsible for late tissue effects, but in conjunction with direct visceral and somatic effects of radiation may further promote late treatment events.

Radiation related tissue effects on the musculoskeletal system among pediatric patients have been mostly anecdotal in nature. The available studies with specific musculoskeletal measurements evaluate a limited number of variables retrospectively and lack correlation with volumetric dosimetry utilized in image-guided radiation therapy, required for accurately assessing radiation related treatment effects. Historic data reported in the literature lacks paired datasets with measurements of the contralateral untreated side, serial studies to adequately delineate the time course of treatment related effects and specifically designed imaging studies to assess effects on the musculoskeletal system. Within the context of this study these variables will be assessed in a prospective manner to establish a baseline for radiation related treatment effects with image-guided radiation therapy. From this protocol we hope to generate objective functions to describe the probability and/or severity of the above listed treatment effects based on radiotherapeutic dose, volume and pretreatment clinical factors. This paradigm has been established at St. Jude in the RT-1 protocol for localized pediatric brain tumors. Specific subjective and objective measurements are listed in table 2.7 below.

Table 2.7

Measurement			
Evaluation		Objective	Subjective
Clinical Physical Ex	amination	Sitting/standing height	Musculoskeletal/Radiation CTC
PT/OT Functional	Evaluation	Measurements of tissue bulk Range of motion Bone length (when available)	Strength
Specific fur	nctional scale	es:	
DASH TESS		Upper extremity function Lower extremity function	
U. of V	/ash. QOL	H&N function	
Diagnostic Imac Standard o	iing f care imagin	g	
qCT Densit	ometry	Treated bone density Bone strength	
3.0 Drug Information – Drug therapy is given on concomitant chemotherapy protocols or a best clinical manageme			omitant management plan.
4.0 Patier	t Eligibility		
4.1	Age ≤ 2	5 years (new enrollments onl	y). No age limit on participants who
4.2	Musculos	skeletal tumor involving the pr	imary site of origin requiring curative
4.3	No prior	therapeutic irradiation at the pri	mary site except for emergent radiation
	dosimetri	cally accounted for in the analys	is.
4.4	Negative for recon	serum or urine β -HCG for females) sents and reenrolled females)	ales of child bearing age (not applicable

Rev 5.2, dated: 6/9/2023 Protocol document date: 6/9/2023

4.5 Patients will be stratified into 2 groups for evaluation of secondary objective endpoints based on the absence or presence of metastatic disease.

Patients may enter this study in specific clinical situations often defined by multimodality protocols that include the use of radiation therapy, including irradiation alone or combined with surgery (following surgical resection that may be macroscopically complete or incomplete, with positive or negative histologic margins) and/or chemotherapy (following neoadjuvant chemotherapy or combined with post-irradiation adjuvant chemotherapy). Patients requiring regional nodal irradiation and/or metastatic site irradiation are allowed as long as the primary site requires radiation. Patients with recurrent tumors or second malignant neoplasms are allowed on this study if the current primary tumor site requiring irradiation has not previously been irradiated. The treatment plan detailed in this study will allow most patients to be concurrently enrolled on institutional and COG studies.

Patients enrolled prior to amendment 4.0, who are still in active participation will be reconsented to the current version of the protocol (4.0). Patients off-study due to completion will be reenrolled on protocol version 4.0 to complete the 7/8 year, 10/11 year and adulthood (18 years of age) requirements. All patients will now follow the same follow-up schedule and procedures as outlined in Table 8.1.

5.0 Treatment Plan

5.1 Overview

Eligible patients will be accessioned at the time of irradiation and undergo a preradiotherapy evaluation, treatment planning, image-guided radiotherapy delivery and intra- and post-irradiation evaluations. Imaging studies obtained for other clinical protocols or routine clinical management may be accepted for use prior to, during or following radiation therapy on this study. Table B1 (appendix B) indicates which studies are considered "standard of care" and which are for research purposes only.

Table 5.1

Treatment Planning and Evaluation Schedule for All Patients

Evaluation Schedule	Pre-IGRT ¹	week 1	week 2	week 3	week 4	week 5	week 6	week 7
Clinical Physical Examination	х	X ²	х	х	х	х	х	х
Physical / Occupational Therap Functional Evaluation	у Х	X1	-	-	-	-	X ³	-

¹ Pre-IGRT includes the interval of time 4 weeks prior to the initiation of treatment. Studies for determination of metastatic disease do not need to be repeated if done at diagnosis. Note for patients receiving brachytherapy only, functional evaluation, MRI and PET imaging will follow catheter removal during week 1 in place of Pre-IGRT imaging

²Sitting and standing height only need to be obtained prior to radiation therapy as tolerated by patient. No measurements of height are recorded during irradiation

³ At or following the completion of radiation therapy

6.0 Radiation Therapy

6.1 Equipment for treatment delivery

External beam

- 6.1.1 Megavoltage linear accelerators utilizing 6MV to 21MV photon energies as well as 4 MeV through 21 MeV electron energies
- 6.1.2 Multileaf collimator or cerrobend block shaped fields
- 6.1.3 Immobilization devices for daily positioning for treatment

Brachytherapy

- 6.1.4 Interstitial catheters, custom molds or intracavitary applicators
- 6.1.5 Iodine-125 or Iridium-192 low dose rate or high dose rate sources
- 6.2 Techniques for radiation therapy treatment

External beam

- 6.2.1 Multiple static field conformal techniques with single or multiple field segments
- 6.2.2 Weekly portal imaging
- 6.2.3 All fields treated daily

Brachytherapy

- 6.2.4 Low dose rate or high dose rate source loadings with equal weight or variable weight sources
- 6.2.5 Transverse or longitudinal interstitial catheter placement
- 6.2.6 Low dose rate source loading for interstitial brachytherapy on the fifth post-operative day or later
- 6.3 Radiotherapy Volume and Dose

The gross tumor volume (GTV), clinical target volume (CTV), and planning target volume (PTV) will be delineated for each patient on a treatment planning imaging study (CT with or without MRI) prior to planning treatment. The larger PTV (PTV-1) should be treated first followed by the smaller PTV (PTV-2). The appropriate margins for these volumes are outlined as follows:

- 6.3.1 Ewing's family of tumors
 - 6.3.1.1 Definitive radiotherapy (no surgical resection) GTV1 – Visible gross tumor consisting of bone initially involved with tumor and soft tissue contiguous with the initial tumor prior to radiotherapy (usually post-chemotherapy) defined by physical exam and imaging studies.

CTV1 – This target volume consists of GTV1 with a 1.0 cm anatomic margin of tissue, respecting anatomic barriers that limit tumor spread.

PTV1 – CTV1 with a treatment site and immobilization device specific margin for target motion and daily treatment set-up variation, usually 5 - 10mm. PTV2 - GTV1 with a treatment site and immobilization device specific margin for target motion and daily treatment set-up variation, usually 5 - 10mm.

6.3.1.2 Post-operative radiotherapy (following surgical resection)

GTV1 – The surgical tumor bed consisting of the margin of bone initially involved with tumor and soft tissue contiguous with the tumor prior to surgical resection as defined by physical exam, imaging studies, operative notes, and pathology reports.

CTV1 – This target volume consists of GTV1 with a 1 cm anatomic margin of tissue, respecting anatomic barriers that limit tumor spread.

PTV1 – CTV1 with a treatment site and immobilization device specific margin for target motion and daily treatment set-up variation, usually 5 - 10mm.

6.3.1.3 Brachytherapy (limited to use in soft tissue Ewing's family of tumors)

GTV1b – The surgical tumor bed defined by intraoperative examination and preoperative imaging studies

CTV1b – This target volume consists of GTV1 with a 1 cm lateral margin and a 2 cm proximal and distal margin relative to the long axis of the tumor for interstitial approaches. For intracavitary and surface brachytherapy applications a margin appropriate for the tumor site and presentation, usually 1-2 cm is recommended.

No PTV exists for brachytherapy procedures.

- 6.3.2 Rhabdomyosarcoma and small round blue cell undifferentiated sarcoma
 - 6.3.2.1 Definitive radiotherapy (no surgical resection)

GTV1 – Visible gross tumor including initially involved soft tissue prior to biopsy or therapy as defined by physical exam and imaging studies.

CTV1 – This target volume consists of GTV1 with a 1 cm anatomic margin of tissue, respecting anatomic barriers of

tumor spread, and regional areas of nodal involvement warranting irradiation.

PTV1 – This volume includes the CTV1 with a treatment site and immobilization device specific margin for target motion and daily treatment set-up variation, usually 5 - 10mm.

PTV2 – This volume includes the GTV1 with a treatment site and immobilization device specific margin for target motion and daily treatment set-up variation, usually 5 - 10mm.

6.3.2.2 Post-operative radiotherapy (following surgical resection)

GTV1 – The post-operative tumor bed consisting of the initially involved soft tissue contiguous with the initial tumor prior to any therapy as defined by physical exam and imaging studies.

CTV1 – This target volume consists of GTV1 with a 1 cm anatomic margin of tissue, respecting anatomic barriers of tumor spread, and regional areas of nodal involvement warranting irradiation.

PTV1 – This volume includes the CTV1 with a treatment site and immobilization device specific margin for target motion and daily treatment set-up variation, usually 5 - 10mm.

6.3.2.3 Brachytherapy

GTV1b – The surgical tumor be defined by intraoperative examination and preoperative imaging studies CTV1b – This target volume consists of GTV1 with a 1 cm lateral margin and a 1 cm proximal and distal margin relative to the long axis of the tumor for interstitial approaches. For intracavitary and surface brachytherapy applications a margin appropriate for the tumor site and presentation, usually 1-2 cm is recommended.

No PTV exists for brachytherapy procedures.

- 6.3.3 Non-rhabdomyosarcoma soft tissue sarcoma (STS)
 - 6.3.3.1 Definitive radiotherapy (no surgical resection) or preoperative radiotherapy*

GTV1 – Visible gross tumor including initially involved soft tissue prior to biopsy or therapy as defined by physical exam and imaging studies.

CTV1 – This target volume consists of GTV1 with a 1.5 cm anatomic margin of tissue, respecting anatomic barriers of tumor spread.

PTV1 – The CTV1 with a treatment site and immobilization device specific margin for target motion and daily treatment set-up variation, usually 5 - 10mm.

6.3.3.2 Post-operative radiotherapy (following surgical resection)

GTV1 – The post-operative tumor bed consisting of the initially involved soft tissue contiguous with the initial tumor prior to any therapy as defined by physical exam and imaging studies.

CTV1 – This target volume consists of GTV1 with a 1.5 cm anatomic margin of tissue, respecting anatomic barriers of tumor spread.

PTV1 – This volume includes the CTV1 with a treatment site and immobilization device specific margin for target motion and daily treatment set-up variation, usually 5 - 10mm.

6.3.3.3 Brachytherapy

GTV1b – The surgical tumor be defined by intraoperative examination and preoperative imaging studies

CTV1b – This target volume consists of GTV1 with a 1 cm lateral margin and a 1.5 cm proximal and distal margin relative to the long axis of the tumor for interstitial approaches. For intracavitary and surface brachytherapy applications a margin appropriate for the tumor site and presentation, usually 1-2 cm is recommended.

No PTV exists for brachytherapy procedures.

6.3.4 Other musculoskeletal tumors

6.3.4.1 Patients receiving radiotherapy for osteosarcoma will receive radiotherapy according to the volumetric and dosimetric guidelines given for Ewing's sarcoma given in section 6.3.1 and table 6.3.1. Patients receiving radiotherapy for other musculoskeletal tumors will receive radiotherapy according to the volumetric and dosimetric guidelines given for soft tissue sarcomas given in section 6.3.3 and table 6.3.3.

The radiation dose will be prescribed to the ICRU reference point, with the target volume minimum and maximum doses being recorded.

Total radiation doses recommended are disease specific and are designed to be consistent with current and proposed institutional and national protocols.

Table 6.3.1

Ewing's sarcoma family of tumors*

Volume Dose

Cumulative Dose

St. Jude Children's Research Hospital IRB NUMBER: RTSARC IRB APPROVAL DATE: 07/13/2023

Rev 5.2, dated: 6/9/2023 Protocol document date: 6/9/2023

Definitive radiotherapy

Primary tumor <8cm PTV1 (GTV1 + CTV1) PTV2 (GTV2)	4500 cGy 1080 cGy	4500 cGy 5580 cGy
Primary tumor ≥ 8cm PTV1 (GTV1 + CTV1) PTV2 (GTV2)	4500 cGy 1980 cGy	4500 cGy 6480 cGy
Post-operative radiotherapy PTV1 (GTV1 + CTV1)	5040 cGy	5040 cGy
Post-operative brachytherapy and External beam radiotherapy CTV1b (brachytherapy) PTV1 (GTV1 + CTV1 + CTV1b)	1500 – 2500 cGy 4500 cGy	1500 – 2000 cGy 6000 – 7000 cGy

Table 6.3.2

Rhabdomyosarcoma and undifferentiated sarcoma**

	Volume Dose	Cumulative Dose
Definitive radiotherapy PTV1 (GTV1 + CTV1) PTV2 (GTV2)	3600 cGy 900 – 1440 cGy	3600 cGy 4500 – 5040 cGy
Post-operative radiotherapy PTV1 (GTV1 + CTV1)	3600 cGy	3600 cGy
Post-operative brachytherapy CTV1b (brachytherapy)	2100 cGy (7 fxn BID)	2100 cGy

Table 6.3.3

Soft tissue sarcoma*

	Volume Dose	Cumulative Dose
PTV1 (GTV1 + CTV1)	6600 – 7000 cGy	6600 – 7000 cGy
Pre-operative radiotherapy PTV1 (GTV1 + CTV1)	4500 - 5580 cGy	4500 - 5580 cGy
Post-operative radiotherapy PTV1 (GTV1 + CTV1)	5580 - 6300 cGy	5580 - 6300 cGy
Post-operative brachytherapy and external beam radiotherapy		
CTV1b (brachytherapy HDR) PTV1 (GTV1 + CTV1 + CTV1b)	1350 cGy (3 fxn BID) 4500 – 5040 cGy	1350 cGy 5850 – 6390 cGy
Post-operative brachytherapy CTV1b (brachytherapy)	3400 cGy (10 fxn BID)	3400 cGy

* Patients receiving radiotherapy for osteosarcoma and other musculoskeletal tumors will receive radiotherapy according to the volumetric and dosimetric guidelines given for Ewing's sarcoma and soft tissue sarcomas respectively.

** RMS dose based on tumor group and stage at diagnosis and immediately prior to radiation defined in section 6.3.2

Rev 5.2, dated: 6/9/2023 Protocol document date: 6/9/2023

The daily radiation fraction size will be 1.8 Gy once daily, with the exception of cases treated with intensity modulation where the microscopic and gross tumor volumes are treated concurrently. In this situation the microscopic tumor daily dose shall be no less than 170 cGy per day.

Brachytherapy cases will be treated with high dose rate techniques where the prescription isosurface will cover the tumor bed (CTV1b) and be delivered at 300-340 cGy per fraction delivered BID.

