2.2.3 Brachytherapy

Brachytherapy is a method of delivering irradiation to a tumor or tumor bed by placing radioactive sources within or adjacent to the target volume. This is usually performed at the time of a surgical resection under direct vision. Planning of the dose to be delivered to the target volume is accomplished after surgery and may utilize CT or MRI imaging studies. In following the model of image-guided radiotherapy, target volumes and critical structures are outlined. The appropriate radioactive source strengths are determined by prospective planning of the dose to be delivered to the target volume and critical structures. Unlike the external beam modalities outlined above, brachytherapy (using low dose rate techniques) is delivered continuously over a period of two to five days, usually while the patient is admitted to the hospital. High dose rate brachytherapy (delivered in moderate 3-5 Gy fractions) will also be used as indicated. Benefits of the high dose rate technique are multiple and include: 1) the ability to better shape dose to the target and away from normal tissue, 2) reduced radiation exposure to family members and staff and 3) delivery of therapy as an outpatient reducing the hassle and cost associated with inpatient hospitalization. Experience with both modalities in patients with sarcomas is limited to smaller pediatric series and moderate sized adult trials. We have had experience with this modality in the pediatric setting as a single adjuvant modality and as a boost dose to external beam radiotherapy. Late toxicity data is not as well studied as compared to conformal radiotherapy or IMRT (34-36).

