- 6.5.4 Treatment plan complexity As treatment plans allow more conformal delivery of radiation to complex target volumes, delivery times and delivery complexity will increase. No objective criteria exist for judging treatment plan complexity, but a less complex plan may be preferable if consistent and reliable delivery is better achieved.
- 6.6 Treatment Delivery

Following completion of treatment planning, the patient will return and undergo verification of position and individual treatment beams. After correct localization of the patient on the treatment couch, radiation therapy will commence. All fields are treated daily at the prescribed dose and fractionation scheme outlined in tables 6.3.1, 6.3.2, and 6.3.3. Localization images are obtained weekly or more often for accuracy of patient positioning. For brachytherapy treatments, following treatment planning, radioactive sources are ordered and catheter placement is again verified, either clinically or radiographically if indicated.

- 6.7 Treatment Related Effects of Radiation
 - 6.7.1 Radiotherapy related treatment effects are both location- and timedependent and clearly related to the dose delivered to specific organs or structures. Effects are divided into acute reactions, early delayed reactions and late reactions divided by arbitrary time periods indicated below.
 - 6.7.2 Acute reactions (during radiotherapy): Hair loss, errythema of skin, desquamation, edema of soft tissues,
 - 6.7.3 Subacute reactions (6 weeks to 3 months after irradiation): Soft tissue edema
 - 6.7.4 Late reactions (more than 3 months after irradiation): Fibrosis of soft tissues including muscle, injury to muscle or bone, including changes in bone growth, and changes in tissue vascularity.
- 7.0 Pretreatment Evaluations

Pretreatment evaluations consist of examinations of physical function, and imaging studies. These studies will also be obtained during and following completion of delivery of radiation (table 5.1, 7.1). Imaging studies obtained pretreatment and during the follow-up period are designed to concur with national and institutional studies.

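### Section 6.3 contains two separate brachytherapy dose inconsistencies: the STS boost (450 cGy per fraction) falls outside the stated 300-340 cGy, and the Ewing's implant is given two upper doses (2500 and 2000 cGy)

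*Combined protocol and SAP*

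**What the plan says.** **Fraction size.** The last paragraph of section 6.3, after Table 6.3.3, states that brachytherapy cases use high dose rate (HDR) technique and will "be delivered at 300-340 cGy per fraction delivered BID". No exception is given. The paragraph just before it, on external beam, does state an exception, for intensity modulation.

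**STS boost.** Table 6.3.3 prescribes the HDR implant combined with external beam as "1350 cGy (3 fxn BID". The cumulative entries for the implant and then the combined course read "1350 cGy 5850 – 6390 cGy".

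**Ewing's implant.** In Table 6.3.1 the volume doses for the implant and then external beam are "1500 – 2500 cGy 4500 cGy". The matching cumulative entries are "1500 – 2000 cGy 6000 – 7000 cGy". This row gives neither a dose rate nor a fraction count. Section 6.3.1.3 restricts the implant: it is "limited to use in soft tissue" Ewing's tumours.

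**Related text.** Section 2.2.3 describes HDR treatment as "delivered in moderate 3-5 Gy fractions". Section 6.6 says: "All fields are treated daily at the prescribed dose and fractionation scheme outlined in tables 6.3.1, 6.3.2, and 6.3.3". Section 6.3.4 describes the total doses as recommended.

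**The concern.** These figures are in the treatment section of a paediatric protocol and are the ones a prescriber would use.

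Read literally, the fraction-size sentence covers the STS boost, yet the boost row implies a larger fraction. Both cannot be followed for the same patient. Section 6.3.4 also sends most other musculoskeletal tumours to Table 6.3.3, so the boost row applies beyond STS.

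The Ewing's row conflicts with itself, because one implant is shown with two upper doses. No rule about whether text or table takes precedence can resolve that.

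What is at stake is clarity and safety of prescription. Dose per fraction and total dose both bear on normal-tissue effects, which the secondary objectives study. The documents do not say how many patients receive either implant.

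**Working it through.** **Inputs.** All come from section 6.3: the fraction-size sentence and Tables 6.3.1, 6.3.2 and 6.3.3. The background fraction range is from section 2.2.3.

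**1. Dose per fraction = total dose / number of fractions**

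| Schedule | Calculation | cGy per fraction | Within 300-340? |
|---|---|---|---|
| Rhabdomyosarcoma, brachytherapy alone (Table 6.3.2) | 2100 / 7 | 300 | yes |
| STS, brachytherapy alone (Table 6.3.3) | 3400 / 10 | 340 | yes |
| STS HDR boost (Table 6.3.3) | 1350 / 3 | 450 | no |

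The two brachytherapy-alone rows reproduce the ends of the stated range exactly. The boost exceeds the upper end by 450 - 340 = 110 cGy, and 110/340 = 32%.

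**2. Can the boost row and the sentence be reconciled?**

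- Three fractions at 300-340 cGy give 900-1020 cGy. That is 330-450 cGy short of 1350 cGy, or 24-33%.
- Keeping 1350 cGy and staying within 300-340 cGy needs between 1350/340 = 3.97 and 1350/300 = 4.5 fractions. The only whole number is 4, at 1350/4 = 337.5 cGy.

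**3. Which boost figures do the documents support?**

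- Total dose: 1350 + 4500 = 5850 and 1350 + 5040 = 6390, which match the printed 5850-6390 cGy. The 1350 cGy total is confirmed.
- Fraction count: these sums do not involve it. Section 2.2.3's 3-5 Gy (300-500 cGy) admits both 450 and 337.5 cGy. The count is not confirmed.

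**4. Ewing's implant: cumulative dose = implant + external beam**

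| Implant dose (cGy) | + 4500 cGy external beam | Printed total |
|---|---|---|
| 1500 (lower end) | 6000 | 6000, agrees |
| 2500 (upper end, volume dose) | 7000 | 7000, agrees |
| 2000 (upper end, cumulative entry) | 6500 | 7000, disagrees |

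In every other course in the three tables, the first component's cumulative dose equals its volume dose. The 1500-2000 cGy entry is the only exception, and it disagrees with both the entry beside it and the total below it.

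**5. Other two-step totals.** 4500 + 1080 = 5580; 4500 + 1980 = 6480; 3600 + 900 = 4500; 3600 + 1440 = 5040. All agree with the tables.

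**The case against.** **The sentence may describe brachytherapy alone.** Its two ends are exactly the two brachytherapy-alone schedules, and the tables label those separately from the combined courses. A prescriber also has a disease-specific row with a total and a fraction count. This is a plausible account of how the sentence arose, but its wording covers brachytherapy cases generally, so it still needs limiting.

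**The tables govern.** Section 6.6 refers delivery to the tables' fractionation, but in a statement about daily fields, which is external-beam language. It does not clearly settle an implant question, and it cannot settle the Ewing's row, where the conflict is within the table.

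**The doses are only recommended.** That word in section 6.3.4 applies to total doses. The fraction-size sentence is mandatory in form.

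**Consequences are small.** This stands. Section 2.1 describes accrual as nearing completion (section 2.5 sets the end at 210 enrolments), implant numbers are not given, and no patient-level harm is shown.

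**Two stronger readings are tempting.**

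- A reader might infer that the boost row is right and the sentence simply omitted it, because the row's totals add up. Those totals support 1350 cGy only. A wrong fraction count (3 for 4) explains the mismatch too.
- A reader might infer that 300-340 cGy per fraction then holds for every other implant, including Ewing's. The documents do not establish this. The Ewing's row is also a combined course and states no dose rate or fraction count, and sections 2.2.3, 6.1.5, 6.2.4 and 6.2.6 still provide for low dose rate sources, for which a twice-daily fraction size has no meaning.

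**Conclusion.** Both inconsistencies are present, and they are independent of each other.

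- **STS boost:** 450 cGy per fraction as tabulated, against a stated maximum of 340 cGy (32% higher). The 1350 cGy total is sound. The documents leave open whether 3 x 450 or 4 x 337.5 cGy is intended. The 32% measures the disagreement between two statements and does not demonstrate an overdose.
- **Ewing's implant:** an upper dose of 2500 or 2000 cGy, giving a combined 7000 or 6500 cGy. The printed total and the volume dose both point to 2500 cGy, so 2000 is probably the wrong figure, subject to the sponsor's confirmation.

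The conclusion assumes only that the printed digits are as the sponsor issued them. Severity is minor. The target local control rates, accrual numbers and monitoring boundaries in section 12.1 do not depend on these figures.

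**What to change.** **STS boost.** The sponsor confirms the intended schedule.

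- If 3 fractions: limit the 300-340 cGy sentence to the brachytherapy-alone schedules, and state 450 cGy x 3, twice daily, for the STS boost.
- If 4 fractions: correct the Table 6.3.3 row to 4 fractions twice daily and leave the sentence unchanged for that row.

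In either case, the 300-340 cGy figure should not be extended to the Ewing's implant unless the sponsor confirms that implant's dose rate and fractionation. Once confirmed, they should be added to Table 6.3.1.

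**Ewing's implant.** Change the cumulative entry to 1500-2500 cGy. If 2000 cGy is the intended ceiling, change the volume dose to 1500-2000 cGy and the combined total to 6000-6500 cGy instead.

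**Cost.** One sentence or one fraction count for the boost, and one table cell for Ewing's (two if 2000 cGy is the ceiling), plus the Ewing's dose rate and fractionation once confirmed. No added patients, procedures or analyses.
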